Problem statement	
Postoperative care of patients undergoing endoscopic sinus surgery (ESS) is important both to minimize discomfort for the patients and to obtain the optimal long-term outcomes. Postoperative sinonasal cavity debridement has been advocated to prevent potential synechiae and sinus ostial stenosis, as well as to improve patient symptoms. Removal of old blood, nasal secretions, crusting, and unabsorbed packing are thought to reduce the inflammatory load, minimize potential for scarring, and allow for improved access of topical medications. However, the debridement procedure can cause bleeding, pain, and discomfort which may interfere with the effective execution of postoperative care.
 
Postoperative formation of adhesions, scarring, synechiae, middle turbinate lateralization, ostial stenosis and edema are major concerns often addressed by the placement of bioresorbable packing intraoperatively. Bioresorbable packing has been demonstrated to decrease the incidence of adhesions and bleeding while improving patient comfort compared to no packing at all. However, bioresorbable nasal dressings, such as PosiSep X, oftentimes have not dissolved by the time of the first postoperative debridement 1-2 weeks after the surgery and therefore need to be removed. The removal of bioresorbable packing during postoperative debridements is usually an uncomfortable experience for the patient. An ideal nasal dressing would optimize both patient comfort as well as wound healing.
 
PuraSinus is a novel topical haemostatic agent based on nanotechnologies in the form of a transparent hydrogel suitable for endoscopic use and for which the use in sinonasal surgery could achieve these various goals. The potential of PuraSinus to enhance endoscopic mucosal wound healing may play a role in optimizing patient comfort during postoperative debridements after ESS. However, clinical evidence on its effectiveness in ESS is limited.
 
We aim to perform a randomized controlled trial to evaluate the efficacy of PuraSinus in improving patient comfort during postoperative debridements among patients who underwent ESS.

Type of Study	prospective, randomized, controlled, single-blinded study.
Study Participants	Patients with chronic rhinosinusitis undergoing bilateral endoscopic total ethmoidectomy receiving standard of care and PosiSep X on one side and PuraSinus in addition to standard of care on the other side. The patients are their own control.
Planned Sample Size	30 patients (over a maximum 12 month recruitment period).
Follow-up duration	All patients will be followed up as per standard clinical care with repeat examination 1 week, 4 weeks, and 12 weeks after surgery.
Planned Study Period	18 months
Primary Objective	
 • To investigate the efficacy of PuraSinus in reducing patient pain during postoperative debridement after ESS compared to PosiSep X.
Secondary Objectives	
 • To assess the time needed to perform postoperative debridements in patients with PuraSinus in their ethmoid cavity after endoscopic sinus surgery • To assess the efficacy of PuraSinus in preventing postoperative complications from endoscopic sinus surgery (adhesions, bleeding, crusting, edema) • To assess the amount of PuraSinus retained in the ethmoid cavity postoperatively • To assess the need for further intervention postoperatively in patients

Primary Endpoint	
 Patient-reported pain (1-10) during postoperative debridement of ethmoid cavity 1 week after surgery
Secondary Endpoints	
 Time required to perform sinonal cavity debridement for ethmoid cavity 1 week after surgery Postoperative healing assessment of mucosal edema, crusting, secretions, and polyps 1 week, 4 weeks, and 12 weeks using validated Lund-Kennedy scoring rubric. Presence of adhesions at 1 week, 4 weeks and 12 weeks. Severity of bleeding during week 1 debridement Amount of residual PuraSinus or bioresorbable dressing in ethmoid cavity 1 week after surgery The need for further intervention postoperatively 4 weeks after surgery as evaluated by an independent blinded reviewer of the video-endoscopy
Intervention (s)	PuraSinus randomized to one ethmoid cavity after bilateral endoscopic sinus surgery and bioabsorbable nasal dressing to the contralateral ethmoid cavity
Inclusion criteria	
 Patient is 18 years of age or older Patient has a clinical indication for and has consented for primary or revision bilateral ESS and had evidence of ethmoid disease bilaterally (Lund-Mackay score at least 1 on each side). Diagnosed with CRS based on American Academy of Otolaryngology – Head and Neck Surgery guidelines
Exclusion criteria	
 Patient has a known history of immune deficiency such as immunoglobulin G or A subclass deficiency, or Human Immunodeficiency Virus (HIV). Patient has concurrent condition requiring active chemotherapy and/or immunotherapy management for the disease (e.g. cancer, HIV, etc.) Patient has clinical evidence of disease or condition expected to compromise survival or ability to complete follow-up assessments during the 90 day followup period. Patient is currently participating in another clinical trial. Patients with known coagulation disorders. Patients with allergies to shellfish.
Study management	The study is an Investigator Initiated Trial sponsored by the University of Southern California. A grant will be provided by 3-D Matrix in the framework of an agreement with the University of Southern California.
Study timelines	
Planned start date: By late 2021
 
End of recruitment latest: By end of 2022
 
End of follow-up period latest: By early 2023
 
End of study latest: By early 2023
 
Study results latest: By mid-late 2023

1.0 BACKGROUND AND HYPOTHESES

Chronic rhinosinusitis (CRS) is one of the most common health problems in the United States and there is evidence that it is increasing in its prevalence and incidence. An estimated 16% of the adult population (>30 million people) is affected annually.¹ Chronic sinusitis causes significant physical symptoms, negatively affects quality of life, and can substantially impair daily functioning. A conservative estimate is that chronic sinusitis results in 18 to 22 million U.S. physician office visits annually, and all forms of sinusitis result in significant health care expenditures.²

The inflammatory response to CRS manifests itself in patient-reported symptoms such as facial pain and pressure, nasal congestion, edema of various local tissues, headache and a variety of other symptoms. Addressing the underlying causes of sinusitis and controlling the symptoms caused by the inflammatory process is the focus of medical therapy. Patients who are recalcitrant to medical therapy may be referred for functional endoscopic sinus surgery (ESS) to improve ventilation and drainage and to remove polyps.

Several hundred thousand ESS procedures are performed in the U.S. annually and this number appears to be increasing. Primary ESS typically involves uncinectomy, ethmoidectomy, maxillary antrostomy, and frontal sinus surgery (sinusotomy). Typical anterior ethmoidectomy involves dissection and removal of the bulla ethmoidalis (the first and most constant ethmoid cell in a highly variable anatomy), anterior ethmoidal cells and agger nasi cells. Complete ethmoidectomy is accomplished by extending the dissection through the basal lamella to reach and remove septations of the posterior ethmoid cells and to reach the sphenoid sinus.

Postoperative care of patients undergoing ESS is important both to minimize discomfort for the patients and to optimize long-term outcomes. Postoperative sinonasal cavity debridement has been advocated to prevent potential synechiae and sinus ostial stenosis, as well as to improve patient symptoms.³ Removal of old blood, nasal secretions, crusting, and unabsorbed packing are thought to reduce the inflammatory load, remove potential for scarring, and allow for improved access of topical medications. However, extensive debridement can cause bleeding, pain, and discomfort which may interfere with the effective execution of postoperative care. Furthermore, debridement is time consuming and may cause mucosal damage and thus delay the postoperative healing process.

Formation of adhesions, scarring, synechiae, middle turbinate lateralization, ostial stenosis and edema are major concerns often addressed by the use of bioresorbable packing postoperatively. Bioresorbable packing has been demonstrated to decrease the incidence of adhesions and bleeding while improving patient comfort compared to no packing at all.⁴ Commonly used bioresorbable packing placed in the middle meatus include chitosan-based nasal dressings such as PosiSep X. Bioresorbable nasal dressings have favorable wound healing characteristics and slowly degrade over time. However, bioresorbable nasal dressings oftentimes have not dissolved by the time of the first postoperative debridement 1-2 weeks after the surgery and therefore need to be manually removed. The removal of bioresorbable packing during postoperative debridements has similar levels of discomfort as the removal of traditional nonresorbable packing.⁵ While bioresorbable packing has advantages in preventing postoperative complications such as adhesions and bleeding, the packing is noticeably uncomfortable to remove for patients during postoperative debridements. An ideal nasal dressing would optimize both patient comfort as well as wound healing.

PuraSinus is a novel topical hemostatic agent based on a self-assembling peptide nanotechnology in the form of a transparent hydrogel suitable for endoscopic use. In otolaryngology, a case series was published by Ananda in 2017 where PuraSinus was applied to the inferior turbinates in 60 patients who underwent endonasal powered turbinoplasty where results were observed for post-operative re-bleeding and adhesion formation. In all 60 patients, no post-operative re-bleeding was observed and there was no adhesion formation.⁶

The hydrogel form of PuraSinus allows the surgeon to only have to apply a thin layer of the product to the surgical site to achieve its desired hemostatic and wound healing effect. This minimizes the amount of the hydrogel needed to be placed into the ethmoid cavity, which in theory would limit the amount of debridement necessary after surgery leading to minimal patient discomfort.

Therefore, we hypothesize that PuraSinus will have less patient discomfort during postoperative debridement compared to traditional bioresorbable packing. We also hypothesize that PuraSinus will have the same incidence of adhesions, bleeding, crusting, edema as PosiSep X.

2.0 OBJECTIVES AND PURPOSE

The objective of this study is to assess the efficacy of PuraSinus in improving postoperative outcomes in patients who undergo endoscopic sinus surgery for chronic rhinosinusitis compared to standard postoperative absorbable packing.

2.1 Primary objective

- To investigate the efficacy of PuraSinus in reducing patient pain during postoperative debridement after endoscopic sinus surgery compared to bioresorbable packing.

2.2 Secondary objectives:

- To assess the time needed to perform postoperative debridements in patients with PuraSinus in their ethmoid cavity after endoscopic sinus surgery
- To assess the efficacy of PuraSinus in preventing postoperative complications from endoscopic sinus surgery (adhesions, bleeding, crusting, edema)
- To assess the amount of PuraSinus retained in the ethmoid cavity postoperatively
- To assess the need for further intervention postoperatively in patients

3.0 STUDY DESIGN

3.1 Type of Study

This is a prospective randomized controlled multicenter study at the University of Southern California that will enroll at least 30 participants who satisfy criteria to compare the efficacy of PuraSinus versus standard of care in patients undergoing endoscopic sinus surgery. The study will utilize an intra-patient control design to assess the safety and efficacy of PuraSinus compared to PosiSep X on the contralateral side. The study patients will undergo PuraSinus placement in one nasal cavity following traditional endoscopic sinus surgery. The study is blinded, meaning that patients will be blinded throughout the study duration to which side received PuraSinus placement. The independent surgeon performing review of the video-endoscopies will also be blinded to which side received PuraSinus.

3.2 Randomization

The patient will undergo a bilateral operation. At the end of the surgery, hemostasis will be performed with bioresorbable nasal packing placed in the ethmoid cavity on one side and PuraSinus in the other ethmoid cavity. The randomization will occur using the concealed envelope method to determine which nostril will receive PuraSinus and which nostril will receive a bioresorbable nasal dressing. The envelope will be opened at the conclusion of the surgery just prior to when hemostasis is about to be performed with PuraSinus and PosiSep X.

3.3 Study outcome measures

3.3.1 Primary outcome

- Patient reported pain (1-10) during postoperative debridement of ethmoid cavity 1 week after surgery

3.3.2 Secondary outcomes

- Time required to perform sinonasal cavity debridement for ethmoid cavity 1 week after surgery
- Postoperative healing assessment of mucosal edema, crusting, bleeding, adhesions and polyps 1 week, 4 weeks, and 12 weeks after surgery
- Amount of residual PuraSinus or bioresorbable dressing in ethmoid cavity 1 week after surgery
- The need for further intervention postoperatively 4 weeks after surgery

4.0 DRUG/DEVICE INFORMATION

PuraSinus belongs to a group called self-assembling peptides. The peptide is a fully synthetic 16-unit oligopeptide termed RADA16 with four repeating amino acid sequences of four amino acids, Arginine (R) – Alanine (A) – Aspartic acid (D) – Alanine (A). The synthetic origin of the material can eliminate the potential risk of infections observed with the existing haemostatic agents that contain animal-derived products. The PuraSinus

peptide is in the form of a 2.5% aqueous acidic solution that is safe, non-biogenic, biocompatible, resorbable, sterile filtered and aseptically filled. The product may be used within a sterile field during surgical procedures.

Under physiological conditions (pH approximately 7, in the presence of Na^+ and K^+ ions) PuraSinus forms a gel similar to collagen fiber structure when it comes into contact with blood or bodily fluid. The gel forms a transparent scaffold which plugs the open micro-vessels leading to hemostasis. The transparent nature of the gel allows the practitioner to visualize the state of hemostasis and allows for easy application of additional therapy if required (figure 1).

Figure 1: PuraSinus® hydrogel

PuraSinus is currently available in 3ml and 5ml syringes (Figure 2). The syringe is connected to an appropriately sized nozzle for direct application to the targeted tissue.

[figure not shown]

Figure 2: PuraSinus® syringe

The gel is applied to the bleeding site in liquid form and is colorless and completely clear enabling continuous monitoring of the bleeding site. It is thus a product well designed for use during surgical and endonasal endoscopic procedures.

5.0 SELECTION AND WITHDRAWAL OF SUBJECTS

The study population will comprise of adult patients with chronic rhinosinusitis scheduled to undergo bilateral total ethmoidectomy in whom placement of PuraSinus is both feasible and medically appropriate.

5.1 Inclusion Criteria:

- a. Patient has provided written informed consent using a form approved by the reviewing IRB.
- b. Patient is 18 years of age or older
- c. Patient is willing and able to comply with protocol requirements.
- d. Patient has a clinical indication for and has consented for primary or revision bilateral ESS and had evidence of ethmoid disease bilaterally (Lund-Mackay score at least 1 on each side).
- e. Patient can tolerate general anesthesia.
- f. Diagnosed with CRS based on American Academy of Otolaryngology – Head and Neck Surgery guidelines

Surgical Inclusion Criteria:

g. Patient underwent an endoscopic total ethmoidectomy bilaterally that is performed with the same surgical technique.

5.2 Exclusion Criteria

- a. Patient has a known history of immune deficiency such as immunoglobulin G or A subclass deficiency, or Human Immunodeficiency Virus (HIV).
- b. Patient has concurrent condition requiring active chemotherapy and/or immunotherapy management for the disease (e.g. cancer, HIV, etc.)
- c. Patient has clinical evidence of disease or condition expected to compromise survival or ability to complete follow-up assessments during the 90 day followup period.
- d. Patient is currently participating in another clinical trial.
- e. Patient has a known coagulation disorder.
- f. Patient is allergic to shellfish (contraindication for chitosan-based products).

5.3 Withdrawal Criteria

- a. Patient death
- b. Voluntary withdrawal – patient voluntarily chooses not to further participate in the study
- c. Lost to follow-up: Patient is more than 7 days late to a study visit and 3 documented attempts to contact the patient are unsuccessful. A patient who misses the week 1 or week 4 follow-up visit will be considered lost to follow-up.
- d. In the investigator's opinion, it is not in the best interest of the patient to continue study participation.
- e. Any study patient who does not attend a scheduled follow-up visit should be contacted by site personnel to determine the reason for the missed appointment(s).

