7.0 STUDY AGENT ADMINISTRATION OR INTERVENTION AND TOXICITY MANAGEMENT PLAN

7.1 Treatment Strategy – The treatment phase begins upon introduction of PuraSinus and bioresorbable nasal dressing into the study patient at the time of surgery

a. Patient Preparation – The patient should be prepared for the planned surgical procedure according to standard surgery center procedures

b. Surgical Extent and PuraSinus Placement

- The technique of total ethmoidectomy should be the same on both sides
- Randomization of the ethmoid cavity to treatment assignment using the envelope method will occur after successful completion of total ethmoidectomy.
- PuraSinus must be used according to the Instructions for Use (IFU).
- Bioresorbable hemostatic packing materials (PosiSep X) will be placed in the opposite ethmoid cavity. Bioresorbable packing will be used according to the IFU.

c. Follow-Up Schedule

The follow-up period begins immediately post-treatment (once the patient exits the operating room). The patient will undergo follow-up assessments including endoscopic examination at three (3) post-operative visits at week 1, week 4, and week 12. A postoperative endoscopic debridement of the ethmoid cavities

will be performed bilaterally at week 1. A second debridement during week 4 is performed if clinically necessary as determined by the surgeon. Risks associated with debridement and nasal endoscopy include possible pain, bleeding, discomfort, irritation, headache, and sneezing.

An overview of the assessments to be performed at baseline and each follow-up interval along with required timing is provided in Table 1. Protocol-required visits occurring outside of the specified date range will be considered and reported as protocol deviations.

7.3 Criteria for removal from treatment (such as undue toxicity, progression of disease, etc.)

7.31 A patient may always be removed from treatment whenever he/she wishes.

7.4 Ancillary treatments.

7.41 Any ancillary treatment of the ethmoid cavity with steroid-eluting stents will not be allowed. If steroid-eluting stents are placed in the ethmoid cavity due to clinical indication, that participant will be excluded from the study.

7.42 Ancillary treatment with oral antibiotics, oral steroids, nasal saline irrigations, or topical steroids as part of standard postoperative care is allowed.

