The study monitor will maintain contact with investigators and study coordinators by phone, email, or on-site visits. Monitoring will be performed concurrently during the period of patient enrollment to completion of the final patient follow-up visit. The frequency of monitoring may occur as often as a biweekly basis. Monitoring will ensure continued protocol compliance and accurate reporting of data, adverse events, protocol deviations and product accountability.

9.0

CLINICAL AND LABORATORY EVALUATIONS AND STUDY CALENDAR

All visits will occur during typical standard of care appointments for patients undergoing endoscopic sinus surgery.

Parameter	Pre-Surgery	Surgery	Week 1	Week 4	Week 12
Sociodemographic Questionnaire, informed consent	X				
Randomization: placement of PuraSinus		X			
Nasal endoscopy video recording			X	X	X
Patient-reported pain during debridement			X		
Endoscopic debridement procedure			X	X ¹	
Time required to perform debridement			X	X ²	
Bleeding			X	X ²	
Review of video-endoscopies by independent blinded surgeon for: 1. Lund-Kennedy score (mucosal edema, crusting, secretions, adhesions, polyps) 2. Residual packing amount 3. Adhesions			X	X	X
Review of video-endoscopy by independent blinded surgeon for: Need for further intervention				X	
Ascertainment of side effects and adverse events		X	X	X	X

Table 1. Study Calendar

¹if clinically indicated.

²if debridement performed

10.0

CRITERIA FOR EVALUATION AND ENDPOINT DEFINITIONS

The outcome status of all eligible patients will be reported. All eligible patients who begin treatment and attend the week 1 postoperative visit will be included in the analysis.

ENDPOINT DEFINITIONS

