10.3 Bleeding During Debridement

The patient will be evaluated during the postoperative week 1 for bleeding during debridement via a recorded nasal endoscopy that will be evaluated by a blinded reviewer. Bleeding will also be assessed at week 4 if a second debridement is performed. The reviewer will grade bleeding during after debridement with the following scale:

Criteria	0	1	2	3
Bleeding	No bleeding	Minimal (confined to the nasal cavity)	Moderate (out of nasal cavity)	Severe (needs repacking or cauterization)

10.4 Postoperative healing assessment of mucosal edema, crusting, secretions, adhesions, and polyps

Nasal endoscopies will be recorded of each participant's ethmoid cavity at 1 week, 4 weeks, and 12 weeks and will be reviewed by a blinded reviewer to evaluate the healing of the ethmoid cavity. The reviewer will assess mucosal edema, crusting, secretions, and polyps using the validated Lund-Kennedy Endoscopy score. Adhesions will be evaluated as either present or absent in the middle meatus.

Criteria	0	1	2
Polyps in middle meatus	Absent	Restricted to middle meatus	Beyond the middle meatus
Discharge in middle meatus	Absent	Thin and clear discharge	Thick and purulent
Edema of the middle meatus	Absent	Mild-moderate	Moderate-severe
Crusting in middle meatus	Absent	Mild-moderate	Moderate-severe

Lund-Kennedy Endoscopy score

Criteria	0	1
Adhesions	No adhesion	Present in middle meatus

Adhesions Criteria

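### Section 5.3c defines loss to follow-up in two incompatible ways; read literally, a reachable patient who misses week 4 leaves the study before the week 12 readings

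*Combined protocol and SAP*

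**What the plan says.** Item c under the heading "5.3 Withdrawal Criteria" contains two sentences. The first sets a joint condition for loss to follow-up: "Patient is more than 7 days late to a study visit and 3 documented attempts to contact the patient are unsuccessful". The second reads: "A patient who misses the week 1 or week 4 follow-up visit will be considered lost to follow-up". A missed week 12 visit is not mentioned there. Item e asks the site to contact anyone who misses a visit and find out why.

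Section 7.1c schedules "three (3) post-operative visits at week 1, week 4, and week 12" and treats visits outside the permitted dates as protocol deviations. Section 10.4 states: "Nasal endoscopies will be recorded of each participant's ethmoid cavity at 1 week, 4 weeks, and 12 weeks". Those recordings supply the Lund-Kennedy and adhesion readings. The study calendar (Table 1, section 9.0) has a row for "Ascertainment of side effects and adverse events", marked at surgery and at weeks 1, 4 and 12.

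Section 10.0 fixes who is analysed: "All eligible patients who begin treatment and attend the week 1 postoperative visit will be included in the analysis". Section 8.3.1 keeps every adverse event under observation until it is settled or accounted for. No section describes study visits or data collection after withdrawal.

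**The concern.** The two sentences of 5.3c give different answers for the same patient. Someone who skips week 4 but answers the telephone is not lost under the first sentence and is lost under the second. Because the item is a withdrawal criterion, the natural literal reading is that this patient leaves the study.

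What is at stake is the last planned reading of healing and adhesions. These are secondary outcomes, but section 1.0 hypothesises that the two products have the same incidence of adhesions, bleeding, crusting and edema. Support for a claim of similarity depends on precision, and only 30 patients are planned. Each patient is their own control, so one withdrawal removes both sides of a pair. If patients who skip week 4 heal differently from those who attend, the remaining week 12 pairs may also be unrepresentative.

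The same sentence covers a missed week 1 visit. Section 8.1.2 gives removal of PuraSinus at week 1 as its reason for not monitoring long-term toxicity. A patient who misses week 1 has not had that debridement as scheduled, yet would drop out of the scheduled adverse event ascertainment at weeks 4 and 12.

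**Working it through.** **1. The plan's own figure.** Section 13.1 gives a mean difference of 2, SD 3.5, two-sided alpha 0.05, 30 subjects, a Wilcoxon signed rank test and 83% power. I took 3.5 as the SD of the paired difference. With the normal-theory efficiency 3/π, the effective n is 30 × 3/π = 28.65. The noncentrality is (2/3.5) × √28.65 = 3.06, and the noncentral t gives 83.9% power. Simulating the signed rank test on normal differences (20,000 runs) gives 84.0%. The stated 83% is reproduced to within about one point. The endpoint is measured at week 1, so a missed week 4 visit does not change this power.

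**2. The text applied to one patient.** The patient attends week 1, misses week 4, is reached by telephone and is willing to attend week 12.

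| Provision | Result |
|---|---|
| 5.3c, first sentence | Not lost: contact succeeded |
| 5.3c, second sentence | Lost: missed week 4 |
| 5.3e | Site asks the reason; the answer does not alter the status |
| 10.0 | Stays in the analysis: attended week 1 |
| Table 1 | Week 12 video, Lund-Kennedy, adhesions and adverse events are due |

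The first two rows cannot both hold. If the second prevails, the last row is not carried out.

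**3. Size.** The documents give no missed-visit rate. I assumed rates of 0% to 20% at week 4, and that every such patient would otherwise attend week 12. The second assumption makes the losses upper bounds at each rate. Pairs left are 30 × (1 − rate), with 28.5 taken as 28. The standard error ratio is √(30/n). The 95% half-width for an assumed adhesion proportion of 10% is 1.96 × √(0.1 × 0.9/n). The one-sided 95% upper bound when no event is seen is 1 − 0.05^(1/n).

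| Assumed week 4 miss rate | Week 12 pairs, n | Standard error ratio | Half-width at 10% | Upper bound, no events |
|---|---|---|---|---|
| 0% | 30 | 1.000 | 10.7 points | 9.5% |
| 5% | 28 | 1.035 | 11.1 points | 10.1% |
| 10% | 27 | 1.054 | 11.3 points | 10.5% |
| 20% | 24 | 1.118 | 12.0 points | 11.7% |

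If only half of the 6 patients at the 20% rate would have come at week 12, the fix would recover 3 pairs. The comparison is then 24 against 27, and the ratio is √(27/24) = 1.061 instead of 1.118.

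**The case against.** The strongest reply is that no section says week 12 data are refused or deleted. Their loss is inferred from placing the sentence among withdrawal criteria. The second sentence could also be meant only to name the visits to which the first applies, so that a reachable patient would not be lost. That reading is possible but less natural, since the second sentence carries no such condition. If it is what was meant, the text still has to say so.

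Several stronger conclusions might be drawn, and the documents do not support them:

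- *Data in hand are thrown away.* Section 10.0 keeps everyone who attended week 1 in the analysis. At most, later data are not collected.
- *Safety follow-up ends.* Section 8.3.1 keeps reported adverse events under observation, and section 9.0 places all visits within standard-of-care appointments. What would be lost is the scheduled study ascertainment of new events.
- *5.3c contradicts 5.3e and 10.0.* Asking a withdrawn patient for a reason is feasible, and a later withdrawal is compatible with an analysis set defined by week 1 attendance. The contradiction lies within 5.3c.
- *A missed week 4 visit has no bearing on week 12.* Section 7.1c allows a second debridement at week 4 where clinically necessary, so a patient who was absent may have missed a step that affects later healing. This calls for a note in the report and does not justify leaving the reading uncollected.

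It is also fair to say that section 13.2 only presents adhesions as proportions, with no paired test. For adhesions the relevant figures are therefore the precision of a proportion, shown in the last two columns of the table.

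**Conclusion.** The concern holds as an internal contradiction in 5.3c. Its literal reading forgoes week 12 healing, adhesion and new adverse event readings from patients who could still be seen. The effect is limited to secondary outcomes and scheduled safety ascertainment; the primary analysis and its power are untouched. At assumed week 4 miss rates of 10% to 20%, at most 3 to 6 of 30 week 12 pairs are lost and standard errors rise by at most about 5% to 12%. These figures rest on assumed rates and on full week 12 attendance by the patients concerned. Bias from non-attendance related to healing is possible, but the documents do not allow it to be sized. The consequence is modest, and the correction is worth making because it costs very little.

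**What to change.** **In 5.3c**, delete the second sentence and keep the contact-based definition in the first. Add wording such as: *A missed visit is recorded as a protocol deviation. Patients who have not withdrawn consent or met another withdrawal criterion continue with the remaining scheduled study visits.*

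**In 10.0**, add the matching clarification. Its present restriction applies to the analysis as a whole, so a bare instruction to use all data obtained would conflict with it for patients who missed week 1. Suggested wording: *Efficacy analyses are limited to patients who attended week 1 and include week 12 data from those who missed week 4. Safety data are reported for all treated patients, including those who missed week 1.*

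**Cost.** The change is a few sentences in two sections. The visits are standard-of-care appointments, and section 11.0 already provides the week 12 gift card. The small downside is that the week 12 readings will include some patients with no week 4 assessment; the report should give their number. The week 4 outcomes of those patients stay missing either way.
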